## **8 Safety monitoring and reporting**

### **8.1 Adverse events**

#### **8.1.1 Definitions and reporting**

An adverse event is defined as the appearance of (or worsening of any pre-existing) undesirable sign(s), symptom(s), or medical condition(s) that occur after patient's signed informed consent has been obtained.

Abnormal laboratory values or test results occurring after informed consent constitute adverse events only if they induce clinical signs or symptoms, are considered clinically significant, require therapy (e.g., hematologic abnormality that requires transfusion or hematological stem cell support), or require changes in study medication(s).

Adverse events that begin or worsen after informed consent should be recorded in the Adverse Events CRF. Conditions that were already present at the time of informed consent should be recorded in the Medical History page of the patient's CRF. Adverse event monitoring should be continued for at least 150 days following the last dose of study treatment. After initiation of new post-treatment antineoplastic therapy, only AEs suspected to be related to study treatment will be collected in the Adverse Events CRF. Adverse events (including lab abnormalities that constitute AEs) should be described using a diagnosis whenever possible, rather than individual underlying signs and symptoms. When a clear diagnosis cannot be identified, each sign or symptom should be reported as a separate Adverse Event.

Adverse events will be assessed according to the Common Terminology Criteria for Adverse Events (CTCAE) version 4.03. If CTCAE grading does not exist for an adverse event, the severity of mild, moderate, severe, and life-threatening, corresponding to Grades 1 - 4, will be used. CTCAE Grade 5 (death) will not be used in this study but is collected as a seriousness criterion. Information about deaths will be collected through a Death form.

The occurrence of adverse events should be sought by non-directive questioning of the patient (subject) during the screening process after signing informed consent and at each visit during the study. Adverse events also may be detected when they are volunteered by the patient (subject) during the screening process or between visits, or through physical examination, laboratory test, or other assessments. As far as possible, each adverse event should be evaluated to determine:

1. The severity grade (CTCAE Grade 1-4)
2. Its duration (Start and end dates)

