3. Its relationship to the study treatment (Reasonable possibility that AE is related: No, Yes)
4. Action taken with respect to study or investigational treatment (none, dose adjusted, temporarily interrupted, permanently discontinued, unknown, not applicable)
5. Whether medication or therapy was given (no concomitant medication/non-drug therapy, concomitant medication/non-drug therapy)
6. Outcome (not recovered/not resolved, recovered/resolved, recovering/resolving, recovered/resolved with sequelae, fatal, unknown)
7. Whether it is serious, where a serious adverse event (SAE) is defined as in [Section 8.2.1](#) and which seriousness criteria have been met.

All adverse events should be treated appropriately. If a concomitant medication or non-drug therapy is given, this action should be recorded on the Adverse Event CRF.

Once an adverse event is detected, it should be followed until its resolution or until it is judged to be permanent, and assessment should be made at each visit (or more frequently, if necessary) of any changes in severity, the suspected relationship to the study treatment, the interventions required to treat it, and the outcome.

Progression of malignancy (including fatal outcomes), if documented by use of appropriate method (for example, as per irRC or as per RECIST), should not be reported as a serious adverse event.

Adverse events separate from the progression of malignancy (example, deep vein thrombosis at the time of progression or hemoptysis concurrent with finding of disease progression) will be reported as per usual guidelines used for such events with proper attribution regarding relatedness to the drug.

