### **8.2.2 Reporting**

For patients who sign the study ICF, SAE collection starts at time of main study informed consent whether the patient is a screen failure or not.

To ensure patient safety, every SAE, regardless of suspected causality, occurring after the patient has provided informed consent and until at least 150 days after the patient has stopped study treatment must be reported to Novartis within 24 hours of learning of its occurrence. If a patient starts a post treatment antineoplastic therapy, then only SAEs suspected to be related to study treatment will be reported.

Any additional information for the SAE including complications, progression of the initial SAE, and recurrent episodes must be reported as follow-up to the original episode within 24 hours of the investigator receiving the follow-up information. An SAE occurring at a different time interval or otherwise considered completely unrelated to a previously reported one should be reported separately as a new event.

Any SAEs experienced after this 150 days period should only be reported to Novartis if the investigator suspects a causal relationship to the study treatment. Recurrent episodes, complications, or progression of the initial SAE must be reported as follow-up to the original episode within 24 hours of the investigator receiving the follow-up information. An SAE occurring at a different time interval or otherwise considered completely unrelated to a previously reported one should be reported separately as a new event.

Information about all SAEs is collected and recorded on the Serious Adverse Event Report Form; all applicable sections of the form must be completed in order to provide a clinically thorough report. The investigator must assess and record the relationship of each SAE to each specific study treatment (if there is more than one study treatment), complete the SAE Report Form in English [For Japan: sites participating in FIH studies must complete the SAE report form in English], and submit the completed form within 24 hours to Novartis. Detailed instructions regarding the submission process and requirements for signatures are to be found in the investigator folder provided to each site.

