#### **10.5.3.2 Adverse events (AEs)**

Primary summary tables for AEs have to include only AEs that started or worsened during the on-treatment period, the treatment-emergent AEs. Additional select summaries will be

produced using all related AEs that started or worsened during the combined on-treatment and post-treatment periods.

The incidence of treatment-emergent AEs (new or worsening from baseline) will be summarized by system organ class and or preferred term, severity (based on CTCAE grades), type of AE, relation to study treatment by treatment group.

Serious adverse events and non-serious adverse events will be tabulated.

All deaths (on-treatment and post-treatment) will be summarized.

All AEs, deaths and serious adverse events (including those from the pre and post-treatment periods) will be listed and those collected during the pre-treatment and post-treatment period will be flagged.

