2.8.1 Adverse events (AEs)

2.8.1.1 Data handling

Adverse events will be coded using the Medical dictionary for regulatory activities (MedDRA) and assessed according to the Common Terminology Criteria for Adverse Events (CTCAE) version 4.03, respectively.

The CTCAE represents a comprehensive grading system for reporting the acute and late effects of cancer treatments. CTCAE grading is by definition a 5-point scale generally corresponding to mild, moderate, severe, life threatening, and death. This grading system inherently places a value on the importance of an event, although there is not necessarily proportionality among grades (a grade 2 is not necessarily twice as bad as a grade 1).

If CTCAE grading does not exist for an AE, grades 1, 2, 3, or 4 corresponding to the severity of mild, moderate, severe, and life-threatening, respectively, will be used. CTCAE grade 5 (death) is not used in this study. Death information will be collected on the “Death” eCRF pages.

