2.8.1.2 Data analysis

Primary summary tables for AEs will include only AEs that started or worsened during the on-treatment period.

The incidence of treatment-emergent AEs (new or worsening from baseline) will be summarized by system organ class and /or preferred tem, severity (based on CTCAE grades),

type of AE and relation to study treatment by treatment group. Serious adverse events and non-serious adverse events will be tabulated.

All deaths (on-treatment and post-treatment) will be summarized. All deaths are considered to be due to study indication.

All AEs collected in the AE (e)CRF page will be listed along with the information collected on those AEs e.g. AE relationship to study treatment, AE outcome etc. AEs starting during the pre or post-treatment periods will be flagged in the listings.

AEs will be summarized by number and percentage of patients having at least one AE in each primary system organ class (SOC) and for each preferred term (PT) using MedDRA coding. Occurrences of an AE will be counted only once in the respective AE category. A patient with multiple CTCAE grades for the same preferred term will be summarized under the maximum CTCAE grade recorded for the event. AE with missing CTCAE grade will be included in the 'All grades' column of the summary tables.

In AE summaries the primary system organ class will be presented alphabetically and the preferred terms will be sorted within primary SOC in descending frequency. The sort order for the preferred term will be based on their frequency in all patients.

The following adverse event summaries will be produced by treatment for AEs starting or worsening during the on-treatment period:

- Overview of adverse events and deaths (number and % of patients who died, with any AE, any SAE, any AE leading to dose reductions/interruptions, AE leading to discontinuation)
- AEs by SOC and PT, summarized by relationship (all AEs and AEs related to study treatment);
- Seriousness (SAEs, and non-SAEs);
- Leading to treatment discontinuation;
- Leading to dose interruption/adjustment;
- Requiring additional therapy;
- Dose limiting toxicities by PT

The following listings will be produced:

- All adverse events (safety set)

Deaths (CSR Outputs)

On-treatment deaths are summarized produced by preferred term.

All deaths will be listed for the safety set, deaths occurring after the on-treatment period will be flagged.

EudraCT and clinicaltrials.gov requirements for AEs and Deaths summaries

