For the legal requirements of clinicaltrials.gov and EudraCT, two required tables on treatment-emergent adverse events which are not serious adverse events with an incidence greater than 5% and on treatment emergent SAEs and SAEs suspected to be related to study treatment will be provided by SOC and PT on the safety set population.

If for a same patient, several consecutive AEs (irrespective of study treatment causality, seriousness and severity) occurred with the same SOC and PT:

- a single occurrence will be counted if there is ≤ 1 day gap between the end date of the preceding AE and the start date of the consecutive AE
- more than one occurrence will be counted if there is > 1 day gap between the end date of the preceding AE and the start date of the consecutive AE

For occurrence, the presence of at least one SAE / SAE suspected to be related to study treatment / non SAE has to be checked in a block e.g., among AE's in a ≤ 1 day gap block, if at least one SAE is occurring, then one occurrence is calculated for that SAE.

The number of deaths resulting from SAEs suspected to be related to study treatment and SAEs irrespective of study treatment relationship, will be provided by SOC and PT.

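### SAP 2.8.1.2 assigns every death to the study indication, which conflicts with the recorded relatedness and fatal-outcome data, with the SAP's own count of deaths from suspected-related SAEs and, if applied to DOR, with the censoring of non-indication deaths

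*SAP*

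**What the plan says.** In the adverse-event analysis text, straight after promising a summary of all deaths, SAP 2.8.1.2 states: "All deaths are considered to be due to study indication". It gives no scope, exception or reason. The matching protocol text, section 10.5.3.2, says only: "All deaths (on-treatment and post-treatment) will be summarized".

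Further down SAP 2.8.1.2, for the EudraCT and clinicaltrials.gov tables, the plan promises by SOC and PT "The number of deaths resulting from SAEs suspected to be related to study treatment and SAEs irrespective of study treatment relationship".

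On data collection, protocol 8.1.1 lists among the items evaluated for each adverse event its relationship to study treatment and "Outcome (not recovered/not resolved, recovered/resolved, recovering/resolving, recovered/resolved with sequelae, fatal, unknown". Protocol 8.2.2 adds: "The investigator must assess and record the relationship of each SAE to each specific study treatment". Protocol 8.1.1 also says that "Progression of malignancy (including fatal outcomes), if documented by use of appropriate method" should not be reported as an SAE.

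For efficacy, SAP 2.7.1 ends DOR at documented progression or at a death due to the study indication. SAP Table 4-2, situation G, censors DOR at the last adequate assessment when a death has another cause. Protocol 14.1.21, 14.1.23, Table 14-5 and 14.1.39 carry the same cause-specific rule.

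**The concern.** A statistical analysis plan should not fix the cause of every death in advance when the case report form collects information bearing on that cause. As written, the sentence overrides investigator-recorded data with an assumption, in a first-in-human study of two checkpoint inhibitors where fatal toxicity is a central safety question.

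Two things are at stake. The first is consistency in reporting deaths: the same patient's death can be described in two ways within one SAP section. The second is DOR, where cause of death decides whether a responder's death is an event or a censoring. The SAP does not say whether the safety sentence reaches that far. If it does, a rule that the SAP and protocol both retain can never apply.

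**Working it through.** The plan gives no figure to reproduce. The check compares the texts, with one small worked example for the direction of the DOR effect.

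**1. Safety reporting.** Take a patient who dies of an SAE that the investigator suspects is related to treatment.

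- Under protocol 8.1.1 and 8.2.2, the record shows a related SAE with a fatal outcome.
- Under the registry-table text in SAP 2.8.1.2, the death is counted under related SAEs.
- Under the blanket sentence in SAP 2.8.1.2, the death is due to the study indication.

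The last line conflicts with the first two, and nothing in the SAP says which attribution governs which output. Protocol 8.1.1 points the same way: documented progression, including fatal progression, is kept out of SAE reporting, so the fatal-SAE count is not meant to be a count of documented progression deaths.

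**2. Where such a death can be seen.** SAP 2.8.1.2 plans an overview of AEs and deaths, on-treatment deaths by preferred term, a listing of all deaths with later ones flagged, an AE listing with relationship and outcome, and the registry count. SAP 2.8 adds selected summaries of related AEs through the post-treatment period. Most toxic deaths therefore remain identifiable.

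The least visible case is a fatal related event that starts more than 30 days after the last dose (for switchers, after the last single-agent dose). It falls outside the on-treatment tables. Grade does not mark it as fatal either: the protocol says "CTCAE Grade 5 (death) will not be used in this study but is collected as a seriousness criterion" and the SAP says "CTCAE grade 5 (death) is not used in this study". The 30-day limits come from protocol 10.5.3.1, not from the sentence at issue.

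**3. DOR, if the sentence is applied there.**

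- Premise: every death is due to the study indication (SAP 2.8.1.2).
- Situation G requires a death from another cause (SAP Table 4-2; protocol Table 14-5).
- Result: no death can meet situation G. A responder who dies without progression becomes an event at the death date, subject to the other rows of the table, where situation G would have censored some of them at the last adequate assessment.
- SAP 4.3.4.3 takes censoring reasons for irRC from the same table, so the consequence carries over.

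**4. Direction of the DOR effect.** The switch changes both the status and the date, so it must be worked through. Take four hypothetical responders, in months from response. A is last assessed at 2 and dies of another cause at 5; B, C and D progress at 3, 4 and 8. The gap for A is 3 months, about 13 weeks, which spans one 8-weekly assessment, so the rule for two or more missed assessments does not apply.

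| Month | A censored at 2 (situation G) | A an event at 5 |
|---|---|---|
| 3 | 2/3 = 0.667 | 3/4 = 0.750 |
| 4 | 2/3 × 1/2 = 0.333 | 3/4 × 2/3 = 0.500 |
| 5 | 0.333 | 1/2 × 1/2 = 0.250 |
| 8 | 0 | 0 |

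Counting the death keeps A in the risk set until month 5. The curve is higher from month 3 to month 5 and lower from month 5 to month 8.

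**5. What does not change.** RECIST PFS counts death from any cause (SAP 2.7.1). ORR and the DLT analysis do not use cause of death. SAE reporting to the sponsor follows protocol 8.2.2, which the sentence does not touch.

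**The case against.** The strongest reply is that the sentence is only a tabulation convention. Death information comes from the Death eCRF pages (SAP 2.8.1.1), while relationship and outcome come from the AE records, so two tables from two sources can coexist. Suspected relatedness means a reasonable possibility, not an adjudicated cause of death, and protocol 8.2.1 asks for an AE or SAE report whenever there is any doubt that an event is due only to the disease. This stands in part: a reader might infer that a death under a suspected-related SAE can never also be a death from the cancer, and the documents do not support that. They do show two attributions with no rule for reconciling them, and a convention that nobody has declared as one.

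Second, a reader might infer that the sentence hides toxic deaths. The outputs listed above largely answer that. The effect on the all-deaths summary depends on whether that table shows cause, and its layout is in the TFL shells document (SAP 1), which is separate from the two documents reviewed.

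Third, the sentence sits in the adverse-event section, and SAP 2.7.1 and Table 4-2 are the specific texts for DOR. Nothing expressly extends the sentence to them, so the DOR consequence must stay conditional. Even so, the shared term leaves the point open, and the SAP gives no other rule for assigning cause of death for DOR.

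Fourth, a reader might infer that counting more deaths as events is conservative for DOR, or can only shorten it. The worked example shows that this is not so.

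**Conclusion.** The point holds as an internal conflict. The blanket attribution has no basis in the protocol and is at odds with the recorded relatedness and fatal outcome and with the SAP's own count of deaths from suspected-related SAEs. If it is applied to DOR, it also empties situation G.

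The size cannot be derived, because neither document gives deaths by cause or by period. If no responder dies of another cause before progression, DOR does not change. Otherwise the curve can move either way. DOR is a secondary endpoint, and under SAP 2.7.2 its Kaplan-Meier estimates are optional, subject to at least 10 responders in each dosing regimen or indication. The DOR part rests on the assumption that the sentence is meant to reach efficacy; the safety-reporting part needs no such assumption.

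**What to change.** - Delete the sentence from SAP 2.8.1.2, or move it to SAP 2.7.1 as an explicitly declared convention for DOR only.
- State one DOR death rule so that SAP 2.7.1, 2.8.1.2 and Table 4-2 agree. Keeping situation G matches the protocol. Counting every death as an event is possible, but should be declared as a deviation, as protocol 14.1.29 requires.
- If the cause-specific rule is kept, say which data source assigns the cause of death.
- In the death summary already planned, identify deaths that have a fatal-outcome AE suspected to be related, including those after the on-treatment period. Show other recorded causes only if the Death eCRF captures them; neither document lists its fields.

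The cost is SAP wording, by amendment before database lock or addendum after it (SAP 1), and a matching change to the table shells and dataset specifications if a row is added. Relatedness and fatal outcome are already collected, so no new data are needed for that row.

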2.8.1.3 Adverse events of special interest / grouping of AEs

An adverse event of special interest is a grouping of adverse events that are of scientific and medical concern specific to compound LAG525. These groupings are defined using MedDRA terms, SMQs (standardized MedDRA queries), HGLTs (high level group terms), HLT (high level terms) and PTs (preferred terms). Customized SMQs (Novartis MedDRA queries, NMQ) may also be used. A NMQ is a customized group of search terms which defines a medical concept for which there is no official SMQ available or the available SMQ does not completely fit the need. It may include a combination of single terms and/or an existing SMQ, narrow or broad. For each specified AESI, number and percentage of patients with at least one event of the AESI occurring during on-treatment period will be summarized.

Summaries of these AESIs will be provided by safety topic and treatment.

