##### **DLT window:**

- Arm A and Arm C with single agent LAG525: 28 days (one cycle) (21 days for patients on Q3W dosing schedule).
- Arm B with combination of LAG525 and PDR001: 56 days (two cycles) (42 days for patients on Q3W dosing schedule).

Emerging data from the new field of immune-immune combination studies suggest that some immune-related adverse events have a prolonged latency ([Wolchok 2013](#)). As such, the DLT window for the combination arm in this trial is extended to the length of two cycles or 56 days.

National Cancer Institute Common Terminology Criteria for Adverse events (NCI CTCAE) version 4.03 will be used for all grading unless otherwise specified. For the purpose of dose-escalation decisions, DLTs will be considered and included in the BLRM.

The investigator must notify the Sponsor immediately of any unexpected CTCAE grade  $\geq 3$  adverse events or laboratory abnormalities. Prior to enrolling patients into a higher dose level, CTCAE grade  $\geq 2$  adverse events will be reviewed for all patients at the current dose level.

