### 6.3.2 Follow-up for toxicities

Patients whose treatment is interrupted or permanently discontinued due to an AE or clinically significant laboratory value, must be followed-up at least once a week (or more if clinically indicated) for 4 weeks, and subsequently at approximately 4-week intervals, until resolution or stabilization of the event, whichever comes first.

The emergence of Immune-Related AE (irAE) may be anticipated based on the mechanism of action of immunomodulatory therapies.

An irAE is any clinically significant adverse event affecting any organ that is associated with study drug exposure, is consistent with an immune-mediated mechanism, and where alternative explanations have been investigated and ruled out or are considered to be unlikely. Serologic, histologic (tumor sample) and immunological assessments should be performed as deemed appropriate by the Investigator or specialist consultant to verify the immune-related nature of the AE. An empiric trial of corticosteroids may also contribute to understanding the etiology of a potential irAE.

Consensus management algorithms for irAEs have been developed and are available to assist investigators in assessing and managing irAEs (refer to [Section 6.3.1](#) Dose modifications).

In case of a toxicity suspected to be a cytokine release syndrome, the assessments outlined in [Section 7.2.2.5.6](#) must be performed.

All patients must be followed up for irAEs, AEs, and SAEs for 150 days following the last doses of LAG525 and/or PDR001.

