2.1.1 General definitions

Study drug and study treatment

For Arm A and C (monotherapy):

Study drug and study treatment both refer to LAG525 and are used interchangeably.

For Arm B (combo therapy):

Study drug refers to the individual compound i.e., LAG525 or PDR001. Study treatment refers to any combination of study drugs.

Date of first/last administration of study drug and study treatment

The date of first (last) administration of study treatment is derived as the first (last) date when a non-zero dose of any component of study treatment was administered and recorded on the Dosage Administration Record (DAR) eCRF. For the sake of simplicity, the date of first (last) administration of study treatment will also be referred as start (last) date of study treatment.

Study day

The study day for all assessments/events will be calculated using the start date of study treatment as reference. For assessments/events occurring on or after the start date of study treatment, study day will be calculated as:

Study day (days) = Event date – Start date of study treatment + 1.

Therefore, the first day of study treatment is study day 1.

For all assessment/events occurring prior to the start of the study treatment, study day will be negative and will be calculated as:

Study day (days) = Event date – Start date of study treatment.

Study day will be displayed in the data listings.

On-treatment assessment/event

An on-treatment assessment/event is defined as any assessment/event obtained in the time interval from the start date of study treatment until the last date of study treatment (i.e., including combination partner) + 30 days inclusive.

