2.8 Safety evaluation

The assessment of safety is based on the type and frequency of Adverse Events (AEs) as well as on the number of laboratory values that fall outside of pre-determined ranges (Common Toxicity Criteria for Adverse Events (CTCAE) grading limits or normal ranges as appropriate). Other safety data include electrocardiogram and vital signs.

The Safety set is used for summaries and listings of safety data with the exception of dose limiting toxicities (DLT) for which the DDS is used.

Differences between treatment received and intended treatment, if any, are provided in a listing.

The overall observation period is divided into three mutually exclusive segments:

1. Pre-treatment period: from day of patient's informed consent to the day before first dose of study medication,
2. On-treatment period: from day of first dose of study medication to 30 days after last dose of study medication,

3. Post-treatment period: starting at Day 31 after last dose of study medication.

Safety summaries are primarily based on all data from the on-treatment period. Following last administration of study medication, adverse events (including serious adverse events), and new antineoplastic therapies are collected for a period of 150 days. Following start of new antineoplastic therapy, only study treatment related adverse events are collected. Select summaries of related adverse events are produced for the overall period starting from the first dose of study treatment until the end of the post-treatment period.

All safety assessments are listed and those collected during the post-treatment period are flagged.

For patients who switch from single-agent LAG525 to combination with PDR001, the on-treatment period is defined from day of first dose of study medication to 30 days after the last dose of single-agent LAG525.

All safety assessments from these patients are listed and the assessments performed under combination and those collected 30 days later than the last dose of single-agent are flagged separately.

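### The AESI table stops 30 days after the last dose although adverse events are collected to 150 days, so a late first AESI enters no specified AESI rate

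*SAP*

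**What the plan says.** **Window for the AESI table.** SAP 2.8.1.3 plans one summary per AESI: the "number and percentage of patients with at least one event of the AESI occurring during on-treatment period will be summarized". SAP 2.8 defines the window as "On-treatment period: from day of first dose of study medication to 30 days after last dose of study medication". SAP 2.1.1 agrees, running it "until the last date of study treatment (i.e., including combination partner) + 30 days inclusive".

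**Window for collection.** SAP 2.8 states that after the last administration "adverse events (including serious adverse events), and new antineoplastic therapies are collected for a period of 150 days". Protocol 6.3.2 names immune-related events: "All patients must be followed up for irAEs, AEs, and SAEs for 150 days following the last doses of LAG525 and/or PDR001". Once new antineoplastic therapy starts, only treatment-related events are collected (SAP 2.8; Protocol 7.1.5).

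**What is promised beyond day 30.** SAP 2.8 promises some summaries of related events that run from first dose through the whole post-treatment segment. Protocol 10.5.3.2 likewise plans further selected summaries "produced using all related AEs that started or worsened during the combined on-treatment and post-treatment periods". SAP 2.8.1.2 lists all adverse events with post-treatment ones flagged, and summarises deaths from both periods. The adverse event summaries itemised in SAP 2.8.1.2 are introduced as on-treatment summaries.

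**What an AESI is.** SAP 2.8.1.3 describes groupings of concern specific to LAG525. It does not list the topics.

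**The concern.** The AESI table is the only place where the SAP specifies a grouped rate per safety topic. Its cut-off comes well before the end of the period over which the trial collects these events. In explaining the length of the combination DLT window, the protocol notes that "some immune-related adverse events have a prolonged latency" (Protocol 6.2.4). A first event in an AESI topic that starts after day 30 would appear in a flagged listing but would add nothing to the rate for that topic.

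At stake is how completely the report describes special-interest harm, mainly for the combination, which is the only treatment enrolled in Phase II (SAP 1.1). The SAP is more generous with time elsewhere. For best overall response it counts assessments up to new antineoplastic therapy because responses may be delayed (SAP 2.7.1), and it uses immunogenicity samples up to 150 days after the last dose (SAP 2.11.1.2).

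**Working it through.** **1. The plan's own figure: 150 days.** The rationale for Protocol Amendment 06 gives a PDR001 half-life of 20 days (90% CI 17 to 23). It takes five times the upper bound and adds a margin of unstated size.

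- 5 × 23 = 115 days; 150 − 115 = 35 days of implied margin.

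The 150 days are consistent with their inputs but cannot be reproduced exactly. The stated reason is pharmacokinetic.

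**2. Post-dose time left out of the AESI table.** 150 − 30 = 120 days; 120 / 150 = 80%. This is a share of collected post-dose days, not of events, and it ignores time on treatment.

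**3. Exposure remaining at the cut-off.** Assuming mono-exponential decline, the residual fraction is 0.5^(t / half-life).

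| Source of half-life | Half-life (days) | Day 30 | Day 150 |
|---|---|---|---|
| PDR001, Amendment 06 | 17 | 29.4% | 0.2% |
| PDR001, Amendment 06 | 20 | 35.4% | 0.6% |
| PDR001, Amendment 06 | 23 | 40.5% | 1.1% |
| PDR001, observed median range, Protocol 1.2.3.2 | 7.2 to 23.8 | 5.6% to 41.7% | 0.0% to 1.3% |
| LAG525, observed median range, Protocol 1.2.3.2 | 7.4 to 15.4 | 6.0% to 25.9% | 0.0% to 0.1% |

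On the half-life used to set the follow-up, about 29% to 41% of the last PDR001 level remains at day 30. On this trial's observed medians the range is wider, about 6% to 42% for PDR001 and 6% to 26% for LAG525. The PDR001 rows do not apply to single-agent patients unless they switched.

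**4. Effect on a reported rate.** The table counts patients with at least one event, so only patients whose first event in a topic falls after day 30 change it. If s is their share among all patients with an AESI in that topic by day 150, then tabulated rate = full-window rate × (1 − s). The documents give neither an AESI rate nor an onset distribution, so both inputs below are assumptions.

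| Assumed s | Full-window rate 10% | Full-window rate 20% |
|---|---|---|
| 0% | 10.0% | 20% |
| 5% | 9.5% | 19% |
| 10% | 9.0% | 18% |
| 20% | 8.0% | 16% |
| 30% | 7.0% | 14% |

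Phase II groups are planned at about 20 patients, extendable to about 40. One late-only patient therefore moves a group's rate by 1/20 = 5 percentage points or 1/40 = 2.5 percentage points.

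**5. Do the promised full-period summaries fill the gap?** They cover related adverse events from first dose to the end of the post-treatment period. Neither document says that they are by AESI topic. SAP 2.8.1.3 sets its own window explicitly, and the general statement in SAP 2.8 does not alter it. An AESI topic pools several coded terms, so a table by system organ class and preferred term does not give the number of patients per topic.

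**The case against.** There is a fair defence of the 30-day window:

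- A rate labelled as on-treatment is a valid on-treatment rate, and Protocol 10.5.3.2 itself makes the primary adverse event tables on-treatment.
- Later data are thinner. Concomitant medication is collected only to the 30-day follow-up or new therapy, later contacts may be by telephone, and unrelated events are no longer collected after new therapy (Protocol 7.1.5).
- Late related events may still be tabulated in the selected full-period summaries, and all late events are listed. The itemised list in SAP 2.8.1.2 is headed as on-treatment, so the absence of full-period tables from it proves little. The separate shells document for tables and listings, which is not among the documents, may contain more.

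The first two points stand as reasons to keep the on-treatment table and to restrict a longer one to related events. The third shows that late events are not lost, but it does not give them an AESI rate.

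A reader might also infer three stronger things that the documents do not support:

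- That follow-up was set at 150 days because immune events come late. The stated reason is the PDR001 half-life; latency is given as the reason for the 56-day combination DLT window only.
- That the rates are in fact understated, or by some particular share. No onset data are given.
- That the AESIs are the immune toxicities. The SAP names no topics. The inference is reasonable, given the immune-mediated profile described for PDR001 in Protocol 1.2.2.2, but it remains an inference.

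**Conclusion.** The point holds as a limited one. A stated rule keeps AESIs starting on days 31 to 150 out of the only AESI table specified, although those events are collected. The tabulated rate for a topic can equal the full-window rate or fall below it, never exceed it. The shortfall is zero if no patient has a first AESI after day 30, and otherwise equals the late-first share, which is unknown. The excluded span is 80% of the collected post-dose days. At its start PDR001 is still present at roughly 6% to 42% of its last level across the half-lives in the documents, assuming mono-exponential decline. The change is worth making because it is cheap and follows the protocol's own plan to summarise related events over the full period. It does not show that the safety conclusions would be wrong.

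**What to change.** - Keep the on-treatment AESI table in SAP 2.8.1.3.
- Add a second AESI table from first dose to last dose plus 150 days, and name it in SAP 2.8.1.2. Restrict it to treatment-related AESIs. If an all-cause version is wanted, cut it at the start of new antineoplastic therapy, because unrelated events are not collected after that.
- Handle patients who switched from single agent to the combination separately. SAP 2.8 already ends their on-treatment period 30 days after the last single-agent dose. Their later events should be shown apart from the single-agent rates.
- State that the AESI groupings also cover PDR001 for the combination groups.

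The cost is SAP wording and one extra table from data already collected. No change to data collection or patient care is involved. The reported full-window rates may be slightly less favourable than the on-treatment ones.
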